After the informed consent (see appendix 1) is taken from each patient who agreed to participate in the study, the participants will be randomly assigned to either an intervention group or a control group. Intervention group will consist of the patients who will receive the educational process (recommendations) about isotretinoin by clinical pharmacists additionally to the usual routine care (education about isotretinoin provided by the physician). Control group will consist of the patients who will receive the usual routine care. Both patients and physicians are unaware of patients' assignment in both groups.

The main task of the clinical pharmacist is to educate patients in intervention group by providing them all information about isotretinoin that can serve the patient during the treatment period, which includes: the degree of the importance of adherence to the drug and the recommendations, the correct method of taking it, the importance, and when, of doing periodic laboratory tests (lipid profile, liver enzyme test, and pregnancy test), and explanation of common side effects, how to avoid and deal with them, and what are the cases in which the drug should be stopped. The detailed information on the recommendation for managing side effects that will be used to educate the patients are provided in Appendix 2.

Patient's adherence to the recommendations, awareness and side effects managements for both groups will be measured through a set of questions adapted from a validated questionnaire after one month and three months of isotretinoin initiation (Appendix 3). The validated questionnaire was adopted from a previous study on patients' knowledge about isotretinoin therapy use in Jordan. The permission to use the questionnaire was obtained from the researcher.

The questionnaire is composed of 41 questions related to: demographics, side effects, physician and clinical pharmacist practice, recommendations and contraindications according to current guidelines, and patients' commitment. In addition, the Hospital Anxiety and Depression Scale (HADS) [22], will be used to evaluate depressive and anxiety symptoms at baseline and during the follow up period in each group. Finally, clinical improvement in acne will be evaluated three months after initiating the treatment from the view of physicians as well as the patients themselves.

Location and safety considerations

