The dermatology clinics located in: King Abdullah University Hospital (KAUH), in Princess Basma Hospital, (PBH), King Talal Hospital (KTH), Princess Haya Hospital (PHH) and Prince Rashid Hospital (PRH) and King Hussein Medical Center will be visited for patients interview and data collection. The participants' privacy will be preserved throughout the study and the participants' answers will be kept strictly confidential and never associated with any personal details. This study does not involve any human biological sample. No potential risks will be associated with the participation in the current study. No special safety consideration for isotretinoin drug Except those mentioned above since it approved from 1982. Consent will be obtained from IRB.

Data analysis

After data was collected, the data was entered into Excel worksheets. The responses were coded and entered into SPSS (version 23). Descriptive statistics of categorical and continuous variables were

calculated. For the categorical variables, the frequency and percentage were calculated, while the arithmetic mean and standard deviation were calculated for continuous variables.

The differences in participants' responses were examined using the Chi-square test (between intervention and control groups) and McNamara's test (between baseline and follow up encounters) for categorical dependent variables as appropriate. For continuous dependent variables, One Way Analysis of Variance (ANOVA) test, independent samples t-test, and Wilcoxon test were performed when applicable. Both Kolmogorov-Smirnov Z and Shapiro-Wilk tests were used to test for normality of continuous variables. The statistical significance level was considered at a p-value ≤ 0.05 .

Patients Knowledge and Awareness of Isotretinoin:

The degree of knowledge and awareness of correct practice was calculated as a total score. The patient knowledge section consisted of ten different questions/items, and each item had two answers (yes/no). Items were coded according to the answer; the correct (adequate) answer was coded as one (1), while the wrong (not adequate) answer was coded as zero (0). So, the knowledge score could take the values of 0 (no knowledge) to 10 (perfect knowledge).

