I adhere to make lipid profile test during isotretinoin use			
yes	102 (99)	98 (98)	0.618
no	1 (1)	2 (2)	
I adhere to use sunblock when going out during isotretinoin use			
yes	98 (95.1)	91 (91)	0.244
no	5 (4.9)	9 (9)	
I adhere to take isotretinoin with fatty foods			
yes	88 (85.4)	62 (62)	< 0.001
no	15 (14.6)	38 (38)	
I adhere not to donate blood during isotretinoin use			
yes	103 (100)	43 (43)	< 0.001
no	0 (0)	57 (57)	
I adhere not to make laser or wax during isotretinoin use			

yes	87 (84.3)	51 (51)	< 0.001
no	16 (15.7)	49 (49)	

Results showed that 86.4% of the intervention group compared to 69% of control group were adherent to the use of eye drop, and the difference was statistically significant (P-value=0.003). The adherence to using body lotion was higher in the intervention group (46.6%) compared to the control group (28%) with a P-value=0.006. On the other hands, there were no significant differences between both groups regarding the use of lip balm and sunblock.

For the two questions about adherence to laboratory monitoring (i.e., the liver function test or the lipid profile test), the rate of adherence was high in both group (99% for the intervention group and 98% for the control group) with no significant statistical difference.

The results of responses to the last three questions about adherence (taking the medication with or after fatty meals, adherence to not donate blood, and not to make laser or wax during treatment) were significantly different between the control and intervention group with P-value <0.001.

5. HADS Scale

HADS-Anxiety score and HADS-Depression score were tested at baseline and at follow-up after three months. At baseline, the mean HADS-Anxiety score for both groups was 7.8079 ± 4.159 , which slightly improved to 7.5862 ± 3.28 at follow-up, which was statistically not significant. Likewise, the mean HADS-Depression score was 6.773 ± 3.709 , while at follow-up it became 7.0148 ± 3.1029 and it was statistically not significant. The responses for intervention and control group at follow-up (intervention vs. control group) are indicated in **Table 6**.

Table 6: HADS anxiety and depression score at follow-up

	Intervention group n (%)	Control group n (%)	P-value
I feel tense or 'wound up.'			
most of the time	4 (3.9)	2 (2)	0.006
a lot of the time	20 (19.4)	7 (7)	
from time to time	54 (52.4)	75 (75)	
not all time	25 (24.4)	16 (16)	
I get a sort of frightened feeling like 'butterflies' in the stomach:			

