In the follow-up questionnaire, multiple additional questions were asked regarding patients' opinion about acne improvement, the impact of side effects on their daily activities, and their satisfaction with the provided drug information. There were statistically significant differences in all these three dimensions between the intervention and control groups.

About 47% of the patients who received the educational process from the clinical pharmacist in addition to the doctor reported that they had an excellent improvement in their acne conditions compared to 30% of the patients who received the educational process from the doctor only, P-value =0.048. Results are shown in **Table 10**.

Table 10: Patient's opinions about the improvement of the acne

	Intervention group n (%)	Control group n (%)	P value
In your opinion, how much is the improvement of your acne			
Excellent	48 (46.6)	30 (30)	0.048
very good	50 (48.5)	56 (56)	
good	5 (4.9)	5 (5)	

There was a significant difference between the intervention group and the control group with regards to the impact of side effects on daily life and normal activities of the patients, P-value<0.001. 76.6% of patients in the intervention group reported no effect or a weak effect on daily activity compared to 48% of the patients in the control group as indicated in **Table 11**.

Table 11: Patient's responses about side effect and their impact on daily activity

	Intervention group n (%)	Control group n (%)	P-value
How does the side effects affect your daily life and your normal activities			
Big impact	0 (0)	4 (4)	< 0.001
Moderate impact	24 (23.3)	48 (48)	
Weak impact	73 (70.9)	46 (46)	
There is no impact	6 (5.8)	2 (2)	

There are three questions about the patient's satisfaction with the provided drug information (either through the usual care provided by the doctor or the additional care provided by the clinical pharmacist in addition to the doctor). There were significant differences between the two groups with more satisfaction for the intervention group; 0% of the intervention group compared to 52% of the control group said they need more explanation about the drug with P-value<0.001. In addition, none of the intervention group compared to 71% of the control group said they need more

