Married women received additional questions. There was a total of seven married women who participated in the study (5 women in the intervention group and 2 women in the control group. All of our sampled married female patients were non-pregnant (100%). Out of them, 71.5% (5 patients); 60% (3 patients) of the intervention group, and 100% (2 patients) of the control group used one type of contraceptive at baseline, after the education process for the intervention group and at follow-up, 100% of patients were using contraception. Referring to contraceptive use during isotretinoin therapy, 0% of the married women in the intervention group and 50% (one patient) in the control group used two different contraceptives. In contrast, after the education process for the intervention group and at follow-up, 100% of patients were using two methods of contraception.

Additionally, no one of the participants reported that they had a pregnancy test every month at baseline. At follow-up, 60% (3 patients) in the intervention group did the pregnancy test monthly compared to no one in the control group. 100% of the participants said that the physician informed them about the teratogenicity of isotretinoin, and they signed a pre-approval sheet before starting the treatment.

Informed consent

Appendix 2

Recommendations for managing side effects:

1- Recommended OTC products for the treatment of common adverse effects

Dry eyes: artificial tears and eye refreshments.

Dry mucus membranes and nose: saline nasal spray and Vaseline.

Dry lips: petroleum lip balm, nonmedicated lip balm.

Dry skin; glycerin-based or lactic acid moisturizing lotion or cream.

Sunburn: choose sunscreen with SPF15 or higher that doesn't contain para-aminobenzoic acid due to drying effect, [2] , and void excessive exposure to the sun because your skin may become more sensitive to sunlight while using the drug, and sunburn may increase [3].

*increase intake of water will decrease the dryness.

2- Isotretinoin causes an elevation of (AST), (ALT) liver enzyme, and (LDH), Triglyceride (TGA) lipid profile, also can lead to pancreatitis. Therefore, monitoring is essential to ensure the safe use of the product, so should be checked before treatment, one month after the start of treatment, then subsequently at three monthly intervals unless more frequent monitoring is indicated [4].

*Reduced intake of junk food and alcohol consumption will control the increase in lipid profile.

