24. Did your doctor request you to sign up consent form which explain to you the isotretinoin side effects?

- Yes

No

25. (In case of using isotretinoin based on medical prescription), the doctor has explained to me the importance of using two contraceptive methods during isotretinoin therapy:

Yes

No

26. Do you think you needed to explain more about the drug in general?

Yes

No

27. Do you think you needed to explain more about the drug in terms of the method of use?

Yes

No

28. Do you think you need edited more explanations about the side effects of the drug and how to avoid it?

Yes

No

29. Do you have any feedback regarding this questionnaire?

Yes

No

Measure of the HADS score:

I'm frustrated.	D	I feel confused.	A
Always	3	Always	3
Often	2	Often	2
Sometimes	1	Sometimes	1
At all	0	At all	0
I'm scared.	A	I still enjoy the things I used to enjoy.	D
Always	3	Always	0
Often	2	Often	1
Sometimes	1	Sometimes	2
At all	0	At all	3
I lost interest in my appearance.	D	I feel kind of afraid something bad is going to happen.	A
Always	3	Always	3
Often	2	Often	2
Sometimes	1	Sometimes	1
At all	0	At all	0
I'd like to have fun and look forward to enjoying things.	D	I can laugh and see the funny side of things.	D
Always	0	Always	0

Often	1	Often	1
Sometimes	2	Sometimes	2
At all	3	At all	3
I suddenly feel shaking.	A	Disturbing thoughts are in my mind.	A
Always	3	Always	3
Often	2	Often	2
Sometimes	1	Sometimes	1
At all	0	At all	0
I can enjoy a book or tv show.	D	I feel happy.	D
Always	0	Always	0
Often	1	Often	1
Sometimes	2	Sometimes	2
At all	3	At all	3
I can sit down easily and feel comfortable.	A	I feel unstable.	A
Always	0	Always	3
Often	1	Often	2
Sometimes	2	Sometimes	1
At all	3	At all	0

B. Follow-up questionnaire

1. Have there been any changes in the dose? (Number of tablets / concentrate)

- Yes
- No

2. What are the results of previous tests?

- LFT: - Normal - high - low
- lipid profile: - normal -high -low

3. Have you been asked to do new tests for this month (after three months of treatment):

- Pregnancy test: - yes - no -not applicable
- Liver function test: - yes -no
- Lipid profile test: - yes -no

4. Do you consult your doctor or pharmacist before using any other medications or dietary supplement during isotretinoin therapy?

- Always 100%
- often 70%

- Sometimes 50%
- Rarely 20%
- Never 0%

5. During your treatment period, did you seek help from outside sources for obtaining information about the medication?

- Yes
- No

- What are the sources?

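### Dose change and liver and lipid results are asked of both arms at follow-up but never analysed, so side-effect impact is reported without dose context and no laboratory results are compared by arm (minor)

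*Combined protocol and SAP*

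**What the plan says.** Follow-up items 1 and 2 in Appendix 3 B ask "Have there been any changes in the dose? (Number of tablets / concentrate" (yes or no) and "What are the results of previous tests" (liver function and lipid profile, each normal, high or low). The Study Protocol applies the questionnaire to both arms and makes side-effect management a measurement aim: "awareness and side effects managements for both groups will be measured through a set of questions adapted from a validated questionnaire".

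The Data analysis section has named analyses for knowledge, adherence to recommendations, HADS and medication adherence. The only text that could reach items 1 and 2 is a general sentence: "The differences in participants' responses were examined using the Chi-square test (between intervention and control groups".

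In the Results, dose appears only as a baseline row of Table 4.1. Laboratory testing appears as whether tests were required and done before treatment (Results 2) and whether patients kept to monitoring (Table 5): "the rate of adherence was high in both group (99% for the intervention group and 98% for the control group". Results 8 states: "There was a significant difference between the intervention group and the control group with regards to the impact of side effects on daily life". Appendix 2, item 2, says that the drug raises liver enzymes and triglycerides and adds: "Therefore, monitoring is essential to ensure the safe use of the product".

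**The concern.** Side-effect impact shows one of the clearer differences between the arms and bears directly on a stated measurement aim. A reader will ask how it arose: through better handling of side effects, through a different dose after randomisation, or both. The form collects a first piece of evidence on this (item 1), and no result uses it.

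Item 2 is similar. The document calls laboratory monitoring essential, and the intervention includes advice on lipids ("Reduced intake of junk food and alcohol consumption will control the increase in lipid profile"). Whether abnormal results were equally common in the two arms is nevertheless not reported, although the question was asked. At stake are the interpretation of a secondary result and a simple safety table. The adherence comparison that drove the sample size is not affected.

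**Working it through.** **1. Table 11 reproduced.** Counts for big, moderate, weak and no impact are 0, 24, 73, 6 (intervention, n = 103) and 4, 48, 46, 2 (control, n = 100). Pearson chi-square = 20.09 on 3 df, P = 0.00016, which agrees with the stated P < 0.001.

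**2. Size of the difference.** Weak or none: (73 + 6)/103 = 76.7% against (46 + 2)/100 = 48.0%, so 28.7 points.
- Standard error = √(0.767 × 0.233/103 + 0.48 × 0.52/100) = 0.065.
- 95% interval = 28.7 ± 1.96 × 6.5 = 15.9 to 41.4 points.

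**3. Dose at baseline (Table 4.1).** Patients at 10, 20, 30, 40 and 60 mg: 2, 26, 14, 60, 1 against 0, 29, 12, 57, 2.
- Chi-square = 2.68 on 4 df, P = 0.612, as stated.
- Mean daily dose = 3420/103 = 33.2 mg against 3340/100 = 33.4 mg.

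The arms started alike, so any dose difference would have to come later. Item 1 is the only question on the form that asks about this.

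**4. What the unused items could show.** No counts are reported for either item, so the missing comparisons cannot be computed. Their precision can be, at assumed rates. The half-width is 1.96 × √[p(1 − p)(1/103 + 1/100)]:
- p = 0.10: 1.96 × √(0.09 × 0.01971) = 8.3 points.
- p = 0.30: 1.96 × √(0.21 × 0.01971) = 12.6 points.

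**5. Limits of the items.**
- Item 1 has no answer option for direction. It also gives no reference period, and Table 4.1 shows patients already up to their fourth month of treatment at baseline, so a 'yes' could refer to a change before enrolment.
- Item 2 relies on the patient's account of undated tests, has no box for a test not done, and has no matching result on the baseline form.

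**6. Table 10 needs reconciling before re-analysis.** The readable control rows sum to 30 + 56 + 5 = 91, although the percentages are out of 100. The form offers two lower grades (acceptable, weak) that the table does not show.
- Printed rows only, 48, 50, 5 against 30, 56, 5: chi-square = 3.77 on 2 df, P = 0.15.
- The 9 controls placed in one lower grade, 48, 50, 5, 0 against 30, 56, 5, 9: chi-square = 13.45 on 3 df, P = 0.004.

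Neither gives the stated P = 0.048. Both tests, like the chi-square for Table 11, ignore the ordering of the answers.

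**The case against.** The strongest reply is that nothing reported is wrong. Results 8 says only that side-effect impact differed between the arms. It does not say why, so no causal claim is left unsupported. A dose change after randomisation would be part of the effect of the intervention and would not confound it. The general chi-square sentence can be read as covering both items, which makes this a gap in reporting and not in design. Other follow-up items are unreported too, and side-effect impact sits under a heading for miscellaneous results. All of this stands, and it is why the point is minor.

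A reader might go further and infer that the intervention arm felt fewer effects because it took less drug. The documents do not support that. In Table 8, 103/103 intervention patients against 98/100 controls never stopped the drug when feeling worse. Fewer intervention patients were classed as non-adherent (12.65% against 23%, P = 0.053). Physicians are said to be unaware of assignment, which makes selective dose changes by prescribers less likely. None of this excludes a dose difference, but it points away from one.

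A reader might also argue that more intervention patients took the drug with fatty food (85.4% against 62%) and so expect worse lipids. Appendix 2 links lipids to junk food and alcohol (item 2). Its advice on fatty meals (item 7) says nothing about lipids.

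What survives is narrower: two relevant questions were put to patients in both arms, and the answers are not shown.

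**Conclusion.** The point holds as a minor one. Items 1 and 2 were collected and not used. As a result, the 28.7-point difference in side-effect impact (95% interval 15.9 to 41.4) has no dose context after baseline, and no laboratory result is compared by arm.

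It would be wrong to conclude that Table 11 is biased or that a strong safety comparison has been withheld. The randomised comparison is valid as a total effect, and patient recall of undated tests can support only a crude check. A low count of dose changes would make dose an unlikely explanation. A high count would leave the matter open, because direction is not recorded as an answer.

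This rests on two assumptions: that answers to items 1 and 2 are on file for most of the 203 patients, and that the assumed 10% and 30% rates are a fair range for the precision quoted.

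**What to change.** 1. Add one descriptive follow-up table by arm: any dose change (direction only where it was written down), liver result and lipid result (normal, high, low, missing). Give risk differences with 95% intervals. State in the table that the answers are patient-reported and undated and have no baseline result.
2. Account for the 9 control patients absent from Table 10 and correct the table or its P-value.
3. Re-analyse Tables 10 and 11 with a proportional-odds model of arm, adjusted for baseline daily dose and treatment month. These are prognostic covariates already in Table 4.1. They do not correct for a later dose change.
4. If Table 11 is split by dose change, label the split as descriptive, because the subgroups are defined after randomisation.

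The cost is a few hours of analysis on data already collected. The drawback is that the data are crude and could exclude only large differences between the arms.
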